#### **7.5.4.8 Concomitant Medications**

Concomitant medications will be reviewed and recorded in the subject's CRF at each study visit, beginning at the Screening visit. Medications (investigational, prescription, over-the-counter, and herbal) and nutritional supplements taken during the 30 days prior to Screening will be reviewed and recorded. At each subsequent visit, change in medications since the previous visit will be recorded. A discussion of concomitant medications is provided in Section [7.4.6](#).

#### **7.5.4.9 Adverse Events**

All AEs will be recorded from the time the subject signs the informed consent through 30 days following the last administration of study drug. The determination, evaluation, reporting, and follow-up of AEs will be performed as outlined in Section 8.5. At each visit subjects will be asked about any new or ongoing AEs since the previous visit. Assessments of AEs will occur at each study visit.

Clinically significant changes from Baseline in physical examination findings, vital signs, clinical laboratory parameters, suicidal ideation and behavior, and ECGs will be recorded as AEs or SAEs, if appropriate. If feasible, additional PK samples will be collected whenever a potentially related SAE occurs.

#### **7.5.4.10 Interim Monitoring Calls**

For additional safety monitoring, the study coordinator will telephone the subject/caregiver between each Extension Period study visit through Week 52. Additional telephone contacts may be made during the Baseline and Treatment Periods as needed. A follow-up call is recommended within 4 weeks following early termination or study completion. The calls will be used to assess AE, discuss any problems or difficulties with treatment, and assess protocol compliance. Study staff will ask about potential adverse effects of study drug including presence of gastrointestinal upset, steatorrhea or frequent loose stools, and weight gain. Staff will inquire about study drug consumption and remaining supply.

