### **7.3.3 Removal of Subjects from Therapy or Assessment**

In accordance with the Declaration of Helsinki, subjects have the right to withdraw from the study at any time for any reason. The investigator and Ultragenyx also have the right to

remove subjects from the study. Ultragenyx must be notified of all subject withdrawals as soon as possible. Ultragenyx also reserves the right to discontinue the study at any time for either clinical or administrative reasons and to discontinue participation of an individual subject or Investigator due to poor enrollment or noncompliance, as applicable.

Subjects will be removed from the study for the following reasons:

- Occurrence of an unacceptable AE
- An illness that, in the judgment of the investigator or Ultragenyx, might invalidate the study or place the subject at risk

Subjects may be removed from the study for the following reasons:

- At the request of the subject, investigator, or Ultragenyx, for administrative or other reasons
- Protocol deviation or unreliable behavior

If the reason for removal of a subject from the study is an AE, the AE and any related test or procedure results will be recorded in the source documents and transcribed onto the Case Report Form (CRF). Each clinically significant abnormal laboratory value or other clinically meaningful abnormality should be followed until the abnormality resolves or until a decision is made that it is not likely to resolve. If such abnormalities do not return to normal within 30 days after the last dose given, their etiology should be identified and Ultragenyx should be notified. All unscheduled tests must be reported to Ultragenyx immediately.

If a subject discontinues from the study prematurely, every reasonable effort should be made to perform the Early Termination Visit procedures within four weeks of discontinuation.

Subjects who withdraw or are removed from the study prior to randomization may be replaced on a case-by-case basis, at the discretion of Ultragenyx.

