#### **7.5.4.6 Pregnancy Testing**

Female subjects of childbearing potential will have urine pregnancy tests at the Screening and Randomization visits and at Weeks 8, 26, and 52 (or Early Termination). Females considered not of childbearing potential include those who have not reached menarche, had total hysterectomy, or have been in menopause for at least one year prior to Screening.

Female subjects with a positive pregnancy test at the Screening visit will not be enrolled in the study; female subjects who become pregnant during the study will be removed from the study. Additional pregnancy tests may be performed at any time in which pregnancy status is in question. A serum pregnancy test will be performed in the event of a positive or equivocal urine pregnancy test result, or can be performed if pregnancy test by urine is not feasible.

Experience with UX007 (triheptanoin) in pregnant women is limited. The study drug may involve risks to a pregnant female or unborn baby which are currently unknown. Sexually active males or females of childbearing potential must use two forms of highly effective methods of contraception during heterosexual intercourse throughout the study period and for 30 days after stopping the study drug. Examples of highly effective methods include:

- Established use of hormonal contraceptives, such as the birth control pill, injection or implant
- Barrier method, such as a condom with spermicide, or cervical cap

- Intrauterine device (IUD) or intrauterine system (IUS), a small device with hormones that goes inside the uterus
- Male sterilization, also called vasectomy
- True abstinence which means not having sex because subject chooses not to (when this is in line with the preferred and usual lifestyle of the subject)

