## 8.5.4 Adverse Event Reporting to Ultragenyx

### 8.5.4.1 General

All AEs (i.e. any new or worsening in severity or frequency of a preexisting condition) with onset after the subject signs consent for study participation must be promptly documented on the AE eCRF via the EDC system. The Principal Investigator is responsible for evaluating all AEs, obtaining supporting documents, and ensuring documentation of the event is adequate. Details of the AE must include severity, relationship to study drug, duration, and outcome.

All AEs will be collected from the time the subject signs informed consent through 30 days following the last dose of study drug. In addition, the Investigator should report any AE that occurs after this time period that is believed to have a reasonable possibility of being associated with study drug.

AEs ongoing at 30 days following the last dose of study drug should have a comment in the source document by the Investigator whether the event has recovered, recovered with sequelae, or stabilized.

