#### **8.5.4.2 Serious Adverse Events, Serious Adverse Drug Reactions, and Requirements for Immediate Reporting**

Any SAE that occurs at any time during the study, including a clinically significantly abnormal laboratory test result that is considered serious, must be reported within 24 hours of knowledge of the event to Ultragenyx or its designee. These requirements apply equally to all subjects, regardless of the study phase or the at-risk subject's treatment assignment or dosage. The reporting requirement for SAEs is from the time of signing of the ICF through 30 days following the last study drug administration.

SAEs will be reported by completing and submitting SAE report forms to Ultragenyx or its designee. Initial SAE reports must be followed by detailed descriptions. These should include copies of hospital case records and other documents when requested. Follow-up SAE information must be submitted in a timely manner as additional information becomes available. All SAEs regardless of relationship to study drug must be followed to resolution or stabilization if improvement is not expected.

A death occurring during the study, during the per-protocol follow-up period, or within 30 days after stopping treatment with the study drug must be reported to Ultragenyx or its designee within 24 hours of knowledge of the death whether or not it is considered treatment-related.

The investigator also must notify the IRB/EC of the occurrence of the SAE, in writing, as soon as is practicable and in accordance with IRB/EC requirements and local law. A copy of this notification must be provided to Ultragenyx or its designee.

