#### **8.5.4.5 Pregnancy in Subject or Partner**

Pregnancies in subjects or partners must be reported within 24 hours of knowledge of the event to Ultragenyx or its designee. The reporting period for pregnancies is the period from the signing of the ICF through 30 days following the last dose of study drug.

Reported pregnancy of a subject or a subject's partner, while participating in the study, will be monitored for the full duration and/or followed until the outcome of the pregnancy is known. In the event of a pregnancy in the partner of a subject, the Investigator should make every effort to obtain the female partner's consent for release of protected health information. Refer to the Study Reference Manual for details on the reporting procedures to follow in the event of pregnancy. Pregnancy-associated SAEs will be processed and submitted, as necessary, as per the SUSAR reporting process (Section [8.5.4.4](#)).

Protocol Number: UX007G-CL201  
Amendment 4 – 30 Nov 2015

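### Adverse events, serious events and pregnancies are to be captured to 30 days after the last dose, but the protocol requires no contact at or after day 30

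*Protocol*

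**What the plan says.** Four protocol sections set the same post-treatment window.

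- Section 7.5.4.9: "All AEs will be recorded from the time the subject signs the informed consent through 30 days following the last administration of study drug".
- Section 8.5.4.1: "All AEs will be collected from the time the subject signs informed consent through 30 days following the last dose of study drug". The same section adds a task at the end of the window: "AEs ongoing at 30 days following the last dose of study drug should have a comment in the source document by the Investigator", saying whether the event has cleared, cleared with residual effects, or settled.
- Section 8.5.4.2: "The reporting requirement for SAEs is from the time of signing of the ICF through 30 days following the last study drug administration".
- Section 8.5.4.5: "The reporting period for pregnancies is the period from the signing of the ICF through 30 days following the last dose of study drug".

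Section 7.5.4.6 gives the contraception requirement the same length: "throughout the study period and for 30 days after stopping the study drug". That is a rule for subjects, not a data-collection window, but it matches the pregnancy reporting period.

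The scheduled contacts are these. Table 2.1 ends with the Week 52/ET visit. Section 7.5.4.9 has subjects asked about AEs at visits, and section 7.5.4.10 runs the interim calls up to Week 52. Beyond that point, section 7.5.4.10 and Table 2.1 footnote 13 both say only: "A follow-up call is recommended within 4 weeks following early termination or study completion". For subjects who stop early, section 7.3.3 adds that "every reasonable effort should be made to perform the Early Termination Visit procedures within four weeks of discontinuation", and section 7.5.1 repeats this.

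**The concern.** A 30-day window works only if someone asks about it at the end. Here the one contact named for completers is recommended rather than required. It has a latest day but no earliest day, and its latest day falls before day 30. The day-30 comment on ongoing AEs therefore has no scheduled contact to supply it. The last pregnancy test is at Week 52/ET, and pregnancy is not among the call topics listed in section 7.5.4.10.

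AE rates are part of a primary objective (protocol section 6). SAP section 8.7.1 puts no upper time limit on treatment-emergent events and divides event counts by observed time to obtain exposure-adjusted incidence. If the 30 days after the last dose were counted as observed time when nobody had asked, those rates would be too low. The period is also of clinical interest: the product is targeted at 35% of daily calories, and sections 7.2 and 7.4.4.1 look for a withdrawal effect when the dose is lowered.

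**Working it through.** The plan states no figure to reproduce, so this is calendar arithmetic.

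**Inputs**

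- Window W = 30 days after the last dose (sections 7.5.4.9, 8.5.4.1, 8.5.4.2 and 8.5.4.5).
- Latest recommended call: 4 weeks × 7 = 28 days after completion or early termination (section 7.5.4.10; Table 2.1 footnote 13).
- ET visit: up to 4 weeks × 7 = 28 days after discontinuation, on a best-effort basis (sections 7.3.3 and 7.5.1).
- Last dose for completers: section 7.5.3 takes a Week 52 blood sample about 90 minutes after food and study drug, so the last dose can fall on the visit day itself.

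**Completers not continuing UX007**

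Let c be the day of the call counted from the Week 52 visit, and d the number of days between the last dose and that visit. The days not reached by any contact are

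u = max(0, 30 − (c + d)).

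| Case | d | c | u |
|---|---|---|---|
| Call on the last recommended day | 0 | 28 | 30 − 28 = 2 |
| Call at one week | 0 | 7 | 30 − 7 = 23 |
| Call on the next day | 0 | 1 | 30 − 1 = 29 |
| No call | 0 | none | 30 |
| Last dose 2 days before the visit, latest call | 2 | 28 | 30 − 30 = 0 |

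The first four rows all comply with the protocol as written.

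**Early discontinuers**

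Take the discontinuation date as the date of the last dose (an assumption), and let e be the day of the ET visit, from 0 to 28.

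- If the 4 weeks in section 7.5.4.10 run from the ET visit, the call falls on day e + c, at most 28 + 28 = 56. Day 30 is covered whenever e + c is at least 30.
- If they run from discontinuation, the latest recommended call is day 28, and 30 − 28 = 2 days remain.
- If the ET visit takes place on day 28 and no call follows, 2 days remain. If neither takes place, all 30 remain.

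The text does not say which starting point applies, and neither contact is guaranteed.

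**Number of subjects**

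Enrolment is about 40. The documents give no rate of entry to the extension study, so the number of completers concerned lies between 0 (all continue) and about 40 (none continue).

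**The case against.** The strongest reply is that the 30-day rules are recording and reporting duties on the investigator, and that such duties need no dedicated visit. The call is a recommendation, so a site that telephones on day 30 or later breaches nothing, and footnote 13 allows further calls as needed. Known problems are followed without a 30-day limit: SAEs to resolution or stabilization (section 8.5.4.2), reported pregnancies to outcome (section 8.5.4.5), and clinically significant abnormalities until they resolve or are judged unlikely to (section 7.3.3). Section 8.5.4.1 also asks for later events thought to be associated with study drug. The Study Reference Manual, to which the protocol refers for further detail on safety assessments, may specify a contact and is not among the documents. The pure timing mismatch is only 2 days.

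Much of this stands, and it rules out three stronger readings that a reader might infer.

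- *The window is never covered, or a compliant site cannot cover it.* The documents do not support this. An ET visit plus a call can reach day 30, as can a latest-day call to a completer whose last dose was 2 or more days before the visit, or any call made later than recommended.
- *Post-treatment events come to light only if the family volunteers them.* This is not so when the call is made, because AE assessment is one of its stated purposes.
- *The loss is greatest in subjects who stop because of an AE.* Nothing shows this. That group has the best-effort ET visit, the recommended call and the open-ended follow-up in section 7.3.3, so the text points the other way.

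The reply does not answer the main point. Open-ended follow-up applies to events the site already knows about, and permission to telephone later does not ensure that anyone does. A window set in the protocol should be supported by the protocol's own schedule.

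**Conclusion.** The point holds in this form: the protocol sets a 30-day post-dose window for AEs, SAEs and pregnancies and a day-30 status note, but requires no contact at or after day 30, so complete ascertainment is not assured. The gap is clearest for completers who do not continue UX007 in the extension study. For them, with the last dose on the Week 52 visit day and 4 weeks read as 28 days, at least 2 days are uncovered if the call is made within the recommended time, more if it is made earlier, and all 30 if it is not made. The optional status of the call matters more than the 2-day mismatch. For early discontinuers the result depends on whether the ET visit and the call take place and on the date from which the 4 weeks are counted.

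The effect is on the completeness of post-treatment safety data. The week 8 efficacy comparison is not touched. How many events would be missed cannot be estimated from the documents. This is a worthwhile and inexpensive improvement to the collection of data for a primary safety objective.

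**What to change.** In section 7.5.4.10 and Table 2.1 footnote 13, and in the copy of that footnote in SAP Appendix B:

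- Make the follow-up call required for every subject not continuing UX007 in the extension study.
- Time it at or shortly after day 30, for example days 30 to 37, counted from the last dose rather than from the visit.
- List what it must ask: new AEs and SAEs, the status of AEs still ongoing and, where applicable, pregnancy.
- Leave an earlier call optional, so that moving the required one does not remove early contact.

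With a completed call at or after day 30 the uncovered tail is max(0, 30 − 30) = 0 days. Sections 7.3.3, 7.5.1, 7.5.4.9, 8.5.4.1, 8.5.4.2 and 8.5.4.5 should be checked for consistency with the revised wording.

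The cost is that one telephone call already in the plan becomes mandatory and each subject's record closes a few days later. No clinic visit is added and treatment does not change.

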#### **7.5.4.11 Dietitian Consultation and Diet Assessment**

Subjects and/or caregivers are required to maintain a record of the subject's daily diet in a diary for the 3 days prior to each visit. The initial 3-day diet history obtained during screening will be used to confirm the subject is not currently on a KD or other high-fat diet, and thereby satisfies requisite inclusion/exclusion criteria. The 3-day diet history recorded prior to randomization will be reviewed by the site dietitian to establish daily caloric intake. The diet diary will be reviewed by study personnel at each visit to the clinic. The dietitian may telephone subjects and/or caregivers, as needed, to provide dietary advice and support. A dietitian consultation will also take place during the Week 2 telephone assessment. Refer to the Study Reference Manual for details on the dietary assessment.

#### **7.5.5 Appropriateness of Measures**

The efficacy parameters to be evaluated in this study encompass the characteristic phenotype observed in Glut1 DS affected individuals, including seizures, delayed neurologic development, and complex movement disorders. The clinical assessments in the study employ standard measures used in other diseases and conditions that impact the central nervous and skeletal muscle systems. EEG and ECG are routine, non-invasive procedures inflicting minimal pain/distress for the subject, while providing relevant indicators of seizure

events and cardiac safety, respectively. The incorporation of overnight EEGs may introduce a level of inconvenience for the subject, however a higher proportion of abnormalities in pediatric Glut1 DS patients were observed in 24-h EEG data compared with routine EEGs (Leary et al. 2003).

Performance measures such as the 6MWT and GMFM-88 have been successfully used in clinical development programs. The 6MWT and GMFM-88 were incorporated into the study design as a performance measure of muscle function to evaluate movement disorders characteristic in Glut1 DS patients. The CNS and CANTAB were included as measures of neurological involvement and cognitive function.

Diaries will be used by subjects and/or caregivers to capture seizure events on a daily basis, thereby minimizing recall bias at site visits. Where possible, additional validated, age-appropriate patient-reported outcomes were included to assess health-related quality of life and activities of daily living (SF-10/SF-12 and PEDI-CAT).

Additional measurements of UX007 and known triheptanoin metabolites will be assessed using blood samples. The panel has been included in this Phase 2 study to provide information on relevant PK parameters following a single-dose and at steady-state. Where possible, timing of assessments has been coordinated with standard safety laboratory tests to minimize risk and discomfort and avoid unnecessary sampling.

The safety parameters to be evaluated in this study include standard assessments such as recording of medical history, AEs and SAEs, physical examination, ECGs, vital signs and weight, serum chemistry, concomitant medications, and other routine clinical and laboratory procedures. Suicidal ideation and behavior will be assessed as an additional safety measure given the central nervous system involvement with Glut1 DS and the likelihood for most if not all subjects to be prescribed at least 1 AED as concomitant treatment.

Since the study will be conducted in a pediatric, adolescent, and adult population, age-appropriate efficacy measures and additional safety measures including interim telephone calls and a DMC have been incorporated into the study design.

## **7.6 Statistical Methods and Determination of Sample Size**

The completeness of the data affects the integrity and accuracy of the final study analysis. Therefore, every effort will be made to ensure complete, accurate and timely data collection, and to avoid missing data.

The procedures for handling missing, unused, or spurious data, along with the detailed method for analyses will be presented in the Statistical Analysis Plan (SAP); in general, missing data will be treated as missing. The information below is intended as a guide to planned analyses. Planned analyses will occur at the end of the double-blind Treatment Period, and at the end of the study (Extension Period).

The statistical analyses will be reported using summary tables, figures, and data listings. Statistical tests will be at one-sided alpha level of 0.05. All analyses and tabulations will be performed using SAS®. Continuous variables will be summarized with means, standard deviations, medians, minimums, and maximums. Categorical variables will be summarized by counts and by percentages of subjects in corresponding categories. All raw data obtained from the CRFs as well as any derived data will be included in data listings.

Each secondary endpoint will be tested independently. No adjustments for multiple comparisons on secondary and exploratory analyses will be performed. The statistical method employed for the analysis of each assessment will be defined in more detail in the SAP.

### **7.6.1 Subject Information**

Summaries and listings will be provided for all subjects who received at least 1 dose of study drug and provided at least 1 safety or efficacy evaluation. Subject disposition summaries will include the number of randomized subjects, the number of subjects receiving study medication, the number of subjects completing the study, and the reasons for discontinuation. Demographic variables include age, sex, and race.

